## 6.2 Selection of pathology practice and pathologists cases

The FDA has provided a table of specific diagnoses, which are to be considered when selecting cases for inclusion in the primary diagnosis study, including organ system, and sample size for particular subtypes and procedures. These are listed in [Table 2](#) below.

**Table 2: FDA List of Cases to be tested for Primary Diagnosis Study**

(TOTAL 2000 CASES FOR THIS EXAMPLE)

CNB = Core Needle Biopsy; TUR = Transurethral Resection; LEEP = Loop Electrosurgical Excision Procedure; Dysp = Dysplasia; ECC = Endocervical Curettage; R/O = Rule Out;

ORGAN	# OF CASES	SUBTYPES (procedures)	
BREAST	300	50	Benign/Atypical CNB
		50	Benign/Atypical Lumpectomy
		50	In-Situ Carcinoma CNB
		50	In-Situ Carcinoma Lumpectomy
		50	Invasive Carcinoma CNB
		50	Invasive Carcinoma Lumpectomy
PROSTATE	300	120	Benign Core Bx
		30	Benign Resection
		120	Adenocarcinoma Bx
		30	Adenocarcinoma Resection
LUNG/BRONCHUS/Larynx/oral cavity/Nasopharynx	100	25	Benign/Inflammatory Bx Only
		25	Dysplasia Bx Only
		30	Carcinoma Bx
		20	Carcinoma Resection
COLORECTAL	150	50	Benign/Inflammatory Bx
		50	Adenomas Including Severe Dysp Bx
		40	Adenocarcinoma Endoscopic Bx
		10	Adenocarcinoma Resection
GE Junction	100	50	R/O Barrett's/Dysplasia Bx
		50	Non-Neoplastic/Inflammatory Bx

**Table 2: FDA List of Cases to be tested for Primary Diagnosis Study**

(TOTAL 2000 CASES FOR THIS EXAMPLE)

CNB = Core Needle Biopsy; TUR = Transurethral Resection; LEEP = Loop Electrosurgical Excision Procedure; Dysp = Dysplasia; ECC = Endocervical Curettage; R/O = Rule Out;

ORGAN	# OF CASES	SUBTYPES (procedures)	
Stomach	100	50	Inflammatory Including R/O H. Pylori Bx
		40	Polyps/ Neoplastic Bx
		10	Polyps/ Neoplastic Resection
SKIN	175	50	Non-Neoplastic/Inflammatory Bx
		50	Squamous/Basal Cell Neoplasms Bx
		75	Melanocytic Lesions Bx
LYMPH NODE (no micrometastases smaller than 0.5 mm)	100	75	For Presence/Absence Of Metastasis
		25	Non-Neoplastic
BLADDER	100	25	Benign/Inflammatory/Non-Neo Bx
		25	Dysplasia Bx
		25	Noninvasive Carcinoma (TUR Or Bx)
		15	Carcinoma TUR/Bx
		10	Carcinoma Resection
Gyn	150	40	Endometrial Bx/Curetting
		10	Hysterectomy for endometrial or cervical cancer
		25	Cervix Bx/Curetting (Bx, ECC)
		25	Cervix Bx/Curetting (Cone/LEEP)
		20	Ovary Benign/Non-Neoplastic
		30	Ovary Neoplastic
LIVER/BD, NEO	50	40	Core Bx
		10	Wedge Bx or Resection
Endocrine	100	ALL COMERS	
		50	Pancreas
		30	Thyroid
		10	Parathyroid
		10	Adrenal
BRAIN/NEURO	60	10	Non-Neoplastic
		25	Neoplastic Bx
		25	Neoplastic Resection
KIDNEY, NEOPLASTIC	50	50	All Comers (Consecutive Cases)
Salivary gland	50	50	
Hernial/Peritoneal	10	10	

**Table 2: FDA List of Cases to be tested for Primary Diagnosis Study**

(TOTAL 2000 CASES FOR THIS EXAMPLE)

CNB = Core Needle Biopsy; TUR = Transurethral Resection; LEEP = Loop Electrosurgical Excision Procedure; Dysp = Dysplasia; ECC = Endocervical Curettage; R/O = Rule Out;

ORGAN	# OF CASES	SUBTYPES (procedures)	
Gallbladder	10	10	
Appendix	10	10	
Soft Tissue Tumors	20	20	
Anus/Perianal	50	50	Bx
Miscellaneous to reach 2000	15	15	

Sponsor should include a sufficient number of difficult and challenging diagnoses in the larger (>100) groups

The total number of cases is to be 2000. The total cases are to be subdivided among the four (4) independent clinical sites (academic, community hospital, and private laboratories.) Each site will be assigned cases consistent with the types of cases read at that site and from the cases listed in [Table 2](#). The cases will be selected from actual cases diagnosed at that practice and taken from that site's own database.

However, it may be impractical for some sites to have sufficient cases of all types required under the protocol. In such eventuality, the PIs will review any gaps in cases enrolled across the study and propose adjustments of allotted cases at certain sites where some unbalance with respect to all numbers of cases for certain sites may occur. However, each site will enroll at least 400 cases and no more than 600 cases.

Ten extra cases at each site will be selected for self-familiarization testing after pathologist training. The selection of these ten cases will follow after the cases for the study have been collected.

### 6.2.1 Inclusion criteria:

Cases are eligible to be included in the study only if all of the following criteria apply:

- Cases originating from and that were diagnosed at that local site
- Cases are available in the site's archive
- Cases are at least 1 year old since accessioning
- Cases are selected because their primary diagnosis is consistent with the assigned target categories listed in [Table 2](#)
- Cases have a set of slides representative of the primary diagnosis for which it has been selected (see below for slide selection criteria).

Slide selection for a given case must meet the following criteria:

- Slide is obtained by surgical pathology and prepared from FFPE human tissue
- Slides must be stained with H&E and accompanying special stains (histochemical and/or immunohistochemical)
- All special stains slides (histochemical and/or immunohistochemical) where the slide and stain is used for diagnosis, not prognosis.

- A chosen slide must demonstrate and be representative of the primary diagnosis; 1 H&E slide selection may suffice for biopsy cases,
- For resection cases, a minimum of 5 H&E slides must be selected, which represent the primary diagnosis. If represented with less than 5 H&E slides, additional H&E slides (primary, secondary, or benign slides) from same case may be used to fulfill minimum number
- Slide is intact, has correct size/thickness, good edges, undamaged coverslip, without pen markings that can't be removed, no air bubbles, tidy labels, and fulfills the quality checks per the general clinical practice

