METHODOLOGY Cases will be selected in consecutive order by the enrolling pathologist starting with cases at least one year old and verified to match inclusion and exclusion criteria, and the case distribution for that site. Upon confirmation of enrollment, the slides necessary to make the diagnosis will be selected and included in the set of slides available to the reading pathologists. Additional slides for the case will be excluded. The original primary diagnosis reported in the clinical file for each case will be the Ground Truth (GT) diagnosis. Each pathologist will read each case enrolled at their site by both conventional light microscope (Glass) and by WSI and record their primary diagnosis only, including the correct subtype of the lesion/neoplasm, and related

parameters (e.g., tumor subtype, tumor grade, margin status, lymph node involvement), if appropriate. The order of reading by Glass or WSI will be randomly determined; and, readings by the two modalities will include a minimum of 4 weeks washout period.

Upon completion of a reading at a site, two independent adjudicating pathologists will compare the primary diagnosis obtained using WSIs and using Glass to the GT diagnosis to determine if there is any discrepancy. Any mismatch will be further judged as major or minor based on pre-specified case rules cited in the literature to categorize a “discordance” into pre-designated categories and to decide if the discordance would have led to a change in patient treatment (i.e., major) or none at all (i.e., minor). If the two adjudicating pathologists do not agree on a “major” discordance, a 3rd independent pathologist shall review the case to determine majority agreement or if a consensus meeting of all three adjudicators is required.

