## 6. INCLUSION AND EXCLUSION CRITERIA

### 6.1 Selection of pathology practice and pathologists

Four sites shall be selected such that:

- There shall be as many as 3 academic and at least 1 community and/or private practice pathology sites,
- The laboratory is accredited by the CAP
- Each site will be assigned cases consistent with the types of cases read at that site and from the cases listed in [Table 2](#). The four sites together shall cover the entire range of cases required in the protocol and are:
  - Ohio State University Wexner Medical Center, Columbus, OH
  - Cleveland Clinic Foundation, Cleveland, OH
  - Washington University Medical Center, St Louis, MO
  - TriCore Reference Laboratories, Albuquerque, NM
- The practice has 4 board certified pathologists to serve as “reader” pathologists to conduct the study for primary diagnosis. The pathologists shall be both specialists and generalists, with acceptable proficiency testing and site performance metrics (e.g. case review rate by tumor board, amended reports) not outside the practice’s norm.

- The practices shall dedicate at least 1 enrolling pathologist (EP) to conduct screening and enrolling cases per inclusion and exclusion criteria, and at least 1 validation enrolling pathologist (VEP) to confirm case enrollment of EP
- Each site shall have at least one dedicated scanning technician properly trained by the sponsor in WSI scanning operations per the sponsor's operator's manual.
- Site can and will conduct the study as approved by the institutional review board (IRB) and in accordance with Good Clinical Practice (GCP) and Human Subjects Protection requirements

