### 8.3 Selection of Case Slides

The site coordinator and/or EP shall search through the site’s database to locate and withdraw from the archive the assigned number of consecutive cases starting with archival cases at least 1 year old since accessioning and moving consecutively back in time. They will choose cases categorized from FDA in

**Table 2.** The EP will screen and enroll cases per the inclusion and exclusion criteria, to record the ground truth primary diagnosis, to record the FDA category information (i.e., organ, procedure, subtype, and category), record the basic patient case note(s) that the reader pathologist will be presented with, to select the slides indicative of primary diagnosis and to collect the supplemental diagnostic information and synoptic checklist information, where available in site pathology report, and relevant to classification, subtype, grade, margin, status, etc. The EP may consult with other pathologists within the site practice who may be subject matter experts in certain case categories, as long as those pathologists are not reader pathologists or VEPs. This supplemental information will be in accordance with truncated CAP cancer protocols (17) developed to highlight the key synoptic information to take into account later when reader pathologist makes study diagnosis.

GT diagnosis is the primary diagnosis based on the original sign-out (reported) primary diagnosis of cases that are enrolled in the study. The ground truth will not be reestablished, and should not include secondary diagnoses. Only a review of the final sign-out report (and not a review of the glass slides) will be used to record this information. The original sign-out primary diagnosis (reported clinically), as well as any supplemental diagnostic information, will be captured verbatim. If site uses synoptic checklists in their pathology report, that information, too, will be recorded.

From those cases, the EP will choose the H&E slide or set of H&E slides in the case that are consistent with the primary diagnosis. The following rules will be followed when selecting slides:

- For biopsy cases, the EP will select at least the H&E slides representative of the primary diagnosis. In most biopsy cases, this can be done with just 1 H&E slide, but the EP may choose more if needed to define the diagnosis. To minimize selection bias, the EP shall select the first H&E slide that encompasses that primary diagnosis.

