## 8.7 Reading a Case

At each site and after appropriate training, four pathologists participating at that site will read the same set of case slides, unique to each site. Each pathologist shall read each case on a conventional light microscope (Reference Method; Glass) and on the Hamamatsu system (Test Method; WSI) in an order randomly determined.

RPs will receive from the site coordinator the slides and/or WSI images to be read. The case study identification, patient age and gender, relevant supplemental clinical history, part and procedure information, and specimen gross description in the EDC system in addition to corresponding slides (either glass or WSI) will be available for RP viewing, but RP will never have access to the final sign-out diagnosis or GT information. Pathologists may not request re-scans of any slide. No additional slides from the case can be requested. Reading Pathologists will not be permitted to order additional re-cuts or stains outside of what was cut/stained during the original clinical review process (i.e., no additional slides will be created for the purpose of this study) and selected by the EP and VEP.

All RPs will perform randomized (read-order) glass and WSI reads with a minimum 4-week washout period between modalities. The order of reading will be randomly assigned such that each case will either be read first using glass slides and LM and then (following a 4-week wash-out period) via WSI or vice versa. All digital reads will be executed using the Hamamatsu Pathology workstation. Pathologists will access the Hamamatsu system via secure login/password. For viewing by glass, the pathologist shall use the light microscope that they normally use at that site.

When the RP reads the cases, all WSI and glass diagnoses, as well as supplemental information based on truncated CAP checklists developed for this study, will be entered into an eCRF using an EDC system.

The RP will write a primary diagnosis in a narrative text in their words.

Next, the reader pathologist shall fill in an abridged CAP checklist to capture supplemental diagnostic information specific to each of the organ malignancy types in the study, if applicable. The abridged checklist will include only those items most relevant to the patient's management, i.e., type, grade, margin and whether infiltration into lymph nodes. The pathologist may use information from an abridged

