## 5.2 Blinding and Unblinding

Glass slides and digital images of slides scanned for each case will be de-identified and coded with a unique study identification number to ensure confidentiality. De-identification will occur per institutional policies/procedures and will follow ‘honest-broker’ policies or comparable institutional practices. All case identification numbers will be unlinked to patient identity and will not be individually identifiable by the reading pathologists.

Reading pathologists will also be blinded to original diagnoses.

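### A reader may re-read a case that he or she signed out, so the reader can be the author of the ground truth, and nothing in the plan identifies or removes such reads

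*Protocol*

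**What the plan says.** Four provisions combine.

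- Source of cases. Protocol 6.2.1 requires "Cases originating from and that were diagnosed at that local site".
- Reference. The Protocol synopsis states: "The original primary diagnosis reported in the clinical file for each case will be the Ground Truth (GT) diagnosis". Section 8.3 adds that it is not re-established: "Only a review of the final sign-out report (and not a review of the glass slides) will be used to record this information".
- Source of readers. Protocol 6.1 makes it a condition of site selection that "The practice has 4 board certified pathologists to serve as" readers.
- Reading. Under Protocol 8.7, "four pathologists participating at that site will read the same set of case slides, unique to each site", each of them in both modalities.

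On blinding, Protocol 8.7 says "RP will never have access to the final sign-out diagnosis or GT information" and SAP 5.2 says "Reading pathologists will also be blinded to original diagnoses". On separation of roles, Protocol 8.3 lets the enrolling pathologist consult colleagues, but only "as long as those pathologists are not reader pathologists or VEPs".

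The exclusions in Protocol 6.2.2 do not mention the signing pathologist. The enrolment eCRF fields listed in Protocol 10.1 do not include that person. Model (1) in SAP 11.1.2 and the further analyses in SAP 11.1.2.1 and 11.1.2.2 have no term or exclusion for a reader's own cases.

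**The concern.** The endpoint is agreement of a reader with a reference. When the reader wrote that reference, part of what is measured is the reader's agreement with himself or herself. The plan recognises that readers should be kept apart from enrolment, but leaves open the more direct link, authorship of the reference.

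The link affects both modalities, which does not make it harmless. In a non-inferiority comparison, an influence that draws both modalities towards the reference also draws their difference towards zero. In addition, the plan judges the WSI rate alone against 7%, and pairing with Glass gives no protection there. What is at stake is the primary comparison and that supportive benchmark. The sample size calculation is not affected.

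**Working it through.** **1. The plan's own figure.** Inputs from Protocol 9.2 and SAP 6: two-sided 5% level, 90% power, margin δ = 0.04, r = 4 readers. Write pW and pG for the agreement rates π'WSI and π'Glass.

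- σ² = [pW(1−pW) + pG(1−pG)] × {1 − λ + (r−1)(ξ−η)} / r
- n = (1.960 + 1.282)² × σ² / (δ + Δ)²

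For pW = 0.6, Δ = −1.5% (so pG = 0.615), λ = 0.5, ξ−η = 0.15: σ² = (0.2400 + 0.2368) × 0.95/4 = 0.1132, and n = 10.507 × 0.1132/0.025² = 1903.7. The plan states 1904. Power at 2000 cases is 91.3%, in line with the plan's claim of more than 90%. The variances are summed here because that form reproduces the table; multiplied, as the formula appears in the text, they give 227.

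**2. The share f of own-signed reads.** The documents do not give it. With one signer per case, at most one of four readers is the author, so f ≤ 25% (2000 of 8000 reads per modality). With equal caseloads, f = 1/(number of signing pathologists in the practice): 1/4 with four, 1/6 with six, 1/20 = 5% with twenty. Practice size is not given either.

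**3. Dilution.** Let own-signed reads keep a fraction k of the true difference. A true excess of 4 points is then observed as 4 × {1 − f(1−k)}, and the chance of declaring non-inferiority is Φ{(0.04 − observed)/SE − 1.96}, nominally 2.5%.

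With major discordance of 8% for WSI and 4% for Glass (assumed; the plan's table stops at 80% agreement), λ = 0.5, ξ−η = 0.15 and 2000 cases:
SE = √{(0.0384 + 0.0736) × 0.95/4/2000} = 0.00365.

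With agreement of 60% for WSI and 64% for Glass, the low end of the plan's table:
SE = √{(0.2400 + 0.2304) × 0.95/4/2000} = 0.00747.

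| Scenario | f = 5% | f = 10% | f = 25% |
|---|---|---|---|
| Observed excess, k = 0 | 3.8 points | 3.6 points | 3.0 points |
| False non-inferiority, 8% vs 4%, k = 0 | 7.9% | 19.4% | 78.3% |
| Observed excess, k = 0.5 | 3.9 points | 3.8 points | 3.5 points |
| False non-inferiority, 8% vs 4%, k = 0.5 | 4.6% | 7.9% | 27.8% |
| False non-inferiority, 60% agreement, k = 0 | 4.5% | 7.7% | 26.7% |

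These use the plan's sample-size variance, not a fit of model (1).

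**4. The opposite direction.** Suppose own reads favour Glass by an extra 1 point, because the reader's glass re-read matches a sign-out made on glass. At 8% vs 4% the false non-inferiority rate becomes Φ(−0.01f/0.00365 − 1.96) = 1.8, 1.3 and 0.4% for the three shares. With an extra 2 points at f = 25%, a true excess of 1.5 points is observed as 1.5 + 0.25 × 2 = 2.0 points, and power at 60% agreement falls from 91% to 76%.

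**5. The 7% benchmark.** At a true WSI rate of 8%, the lowest expected observed rate (no discordance at all on own reads) is 8 × (1−f) = 7.6, 7.2 and 6.0%. If own WSI reads instead have 4% discordance, f = 25% gives 0.75 × 8 + 0.25 × 4 = 7.0%.

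**The case against.** The strongest reply is that the plan already limits memory. Cases are at least one year old and are taken consecutively back in time (Protocol 6.2.1, 8.3), labels are coded (8.5), coverslip markings are removed (8.3), reports are withheld (8.7) and modality order is randomised (SAP 5.1). No modality difference at all on own reads would need near-complete recall of the individual case. Shared thresholds are a different matter: if the image hides a feature, the author of the report misses it too. Removing disagreement between observers could even make an own read a cleaner test of modality. This stands, and it is why the rows with k = 0 are extremes. It does not close the gap, because the reader's thresholds are still built into the reference for those reads.

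The 25% share also requires the four readers to have signed every case at the site, although each site has at least an enrolling and a verifying pathologist besides, who may sign cases too. That stands as well.

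The 7% benchmark gives partial protection. At 8% true WSI discordance, the expected rate stays above 7% for shares of 5 and 10%, but need not at 25%.

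A reader might infer that the blinding statements are false for own cases. The documents do not support that: having written a report more than a year earlier is not access to it.

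**Conclusion.** The gap is real. The documents allow a reader to be the author of the ground truth, and as written the analysis could neither detect nor remove such reads. The share is unknown, between 0 and 25% of reads if one pathologist signs each case; co-signing could raise that ceiling.

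A reader might go further and infer that the design favours non-inferiority, or that the false-positive rate is near 78%. Neither follows. Dilution towards zero is one possible effect; a better match of own glass reads to a sign-out on glass, which the documents do not state, works against WSI. The 78% figure needs both the ceiling share and no modality difference on own reads. At smaller shares, or with half the difference kept, the rate is about 5 to 28%; at 60% agreement with no difference on own reads it is about 4.5 to 27%. The net direction cannot be fixed from the documents. Because the problem is inexpensive to measure and to remove, it merits a change to the plan.

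**What to change.** 1. Record the sign-out pathologist for each case as a study code. Protocol 8.5 has the coordinator store the final pathology report with the case, so where the report names the signer this can also be done after enrolment.
2. Report the share of own-signed reads by site and by reader.
3. Before database lock, pre-specify a fit of model (1) that drops both modality reads of every own-signed reader-case pair, preferably as the primary analysis and at minimum as a sensitivity analysis. Give the 7% comparison on the same reads.
4. Where enrolment is still open and the Table 2 quotas allow, take the next consecutive case in place of one signed out by a reader at the site.

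Cost: one extra field, and at most about one of four reader pairs on affected cases. If every case were affected, r falls from 4 to 3 and the variance factor rises from 0.95/4 = 0.2375 to (0.5 + 2 × 0.15)/3 = 0.2667. In the 1904 cell, power at 2000 cases would then fall from 91.3% to about 88.0% (n = 1903.7 × 0.2667/0.2375 ≈ 2137). Smaller shares cost less.

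Step 4 alters consecutive selection to some degree and may be hard where a reader is the site's specialist for a Table 2 category, so it should not be a blanket exclusion.

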### **6.2.2 Exclusion criteria:**

Cases are excluded from the study if any of the following criteria apply:

- Case does not have relevant slides or if case information necessary for the study is missing
- Case is still active (less than 1 year old) at the local site
- Cases for which the control slides for immunohistochemistry and special stains are not available
- Two cases from same individual
- Gross-only cases that have no slides
- Cases that are frozen section, cytology or hematology or immunofluorescence specimens only
- Case where the only available set of slides have evidence only of secondary or no diagnoses and not the primary diagnosis for which the case is being screened.

Slides for a given case will be excluded if they meet the following criterion:

- Glass slide that is broken, has abnormal size/thickness, beveled edges, poor coverslip (cracks, waviness, scratches), is sticky, has many pen markings or dirt that cannot be removed, contains air bubbles and overhanging labels that can't be corrected, and if stain is severely faded.

